## **Research Methodology**

### **1. Population and Samples**

#### **1.1 Population**

The study will include Thai individuals, both male and female, aged between 40-65 years.

#### **1.2 Sample size**

There is no previous study to reference, the researchers have opted for a pilot study with a sample size of 28 participants.

#### **1.3 Inclusion criteria**

- 1) Gender: Male or female
- 2) Nationality: Thai, capable of reading, writing, and understanding the Thai language
- 3) Age: Between 40 - 65 years
- 4) Not using any facial creams or lotions that may impact the study, such as those with anti-aging effects (e.g., containing Vitamin A, fruit acids, or Hydroquinone)
- 5) Individuals with mild to moderate skin conditions, assessed using the Hyperpigmentation status scale 1-2, and Wrinkle severity grading scale 2-3.
- 6) Willingness to avoid sunbathing and minimize sun exposure during the study period
- 7) Availability for scheduled research team meetings

#### **1.4 Exclusion criteria**

- 1) Individuals with allergies to components tested in the serum
- 2) History of any cancer, especially skin cancer
- 3) Acute or chronic skin conditions causing inflammation, such as Eczema or Atopic dermatitis
- 4) Pregnant women (positive pregnancy test), breastfeeding mothers, or those planning pregnancy during the study

- 5) Individuals who underwent facial procedures (e.g., laser treatments, energy-based devices like focus ultrasound, LED, or Infrared, facial surgeries, filler injections) within the last 3 months before joining the study
- 6) Skin damage in or near the testing area, including sunburn, tattoos, or scars
- 7) Consumption of vitamin supplements and/or hormonal supplements

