#### **5) Skin Cleaning Instructions for Volunteers**

Volunteers are advised to cleanse their skin lightly with the provided soap before testing. Cleaning conditions are standardized to maintain consistency across all tests.

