Positions are determined based on Hamilton's classification of contour changes of facial skin, specifically targeting static wrinkles effectively. Volunteers will calculate the average value for both areas to represent their data. The assessment will be performed by two board-certified dermatologists, each evaluating both areas, ensuring a thorough and reliable evaluation of wrinkle improvement.

The positions for measurements using Visioscan

Visia-CR is utilized as a detailed facial imaging system to compare changes before and after product usage. The assessment is done by comparing images using the Subject Global Aesthetic Improvement Scale (SGAIS) as follows:

Score 1: Worse (no improvement)

Score 2: Mild improvement (<25% improvement)

Score 3: Improvement (25-49% improvement)

Score 4: Much improved (50-74% improvement)

Score 5: Very much improved (75% improvement or more)

The evaluation is conducted by two board-certified dermatologists, each specializing in skin health. The images captured by Visia-CR allow for a thorough comparison of facial conditions before and after product usage, providing a detailed understanding of the product's impact on the skin's aesthetic improvement.

The medical technicians will perform measurements of skin moisture, water loss, skin elasticity, skin color, and capture facial images using a specialized imaging device, taking approximately 30 minutes for each

participant. This research will measure these parameters on the first day (d1) before applying EGF serum to establish a baseline.

7) Baseline Measurements:

Participants will undergo measurements on the first day, assessing moisture, water loss, skin elasticity, skin color, and facial images using Corneometer, Tewameter, Cutometer, and imaging devices.

8) Application of EGF Serum:

Participants will apply EGF serum twice daily for 8 weeks, using three drops each time, covering the entire face.

9) Sunscreen Application:

After using EGF serum in the morning, participants will apply Skin Intelligence Sunscreen Cream SPF30 PA+++, using 2 fingertip units (approx. 1 gram) each time.

10) Second Visit (2 Months):

Participants return for a second assessment after 2 months, with measurements conducted similar to the baseline.

11) Subsequent Visits:

Participants stop using the serum and return for measurements in the 3rd and 4th months, following the same procedure.

Note:

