If adverse events occur or if there are signs of an allergic reaction, participants will cease product usage and receive standard treatment from the institute. Severe reactions may lead to the participant's exclusion from the study.

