### 3. The materials and equipment

**Tested Product:**

Objective: Serum containing 75 ppm Epidermal Growth Factor (EGF)

Composition:

0.5% Acrylate Copolymer (Thickener)

0.5% Triethanolamine (TEA) (Neutralizer)

Phenoxyethanol / Chlorphenesin (Preservative)

Deionized Water (Solvent)

EGF 75 ppm

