**4. Table of activities:**

Activities	Day/wk	d1	2 wk	4 wk	8 wk	12 wk	16 wk
Record data		✓					
Apply EGF serum		✓	✓	✓	✓		
Apply sunscreen cream		✓	✓	✓	✓	✓	✓
Measuring skin moisture and water loss using Tewameter and Corneometer		✓			✓	✓	✓
Measuring skin elasticity using Cutometer		✓			✓	✓	✓
Measuring melanin index using Mexameter		✓			✓	✓	✓
Measuring wrinkle using Visioscan		✓			✓	✓	✓
Capturing facial images using Visia-CR		✓			✓	✓	✓
Evaluation by Specialists (Two Board-Certified Dermatologists)					✓	✓	✓
Assessment of Participant Satisfaction					✓	✓	✓
Assessment of adverse effects					✓	✓	✓

Assessment of adverse effects via videocall application line		✓	✓			
--	--	---	---	--	--	--

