## 7. Statistical Analysis

7.1 Descriptive Statistics for General Participant Information: Descriptive statistics will be used for continuous quantitative data, presenting mean and standard deviation or median and interquartile range (IQR). For non-continuous quantitative data and qualitative data (ordinal scale, nominal scale), results will be reported as percentages.

7.2 Primary Outcome Analysis: The primary outcome data, comparing values for skin moisturization, water loss from the skin, skin elasticity, skin color measurement, and wrinkle assessment before and after using the serum at 8 weeks, 12 weeks, and 16 weeks, will be analyzed. If the data follow a normal distribution, a repeated-measure ANOVA will be used, with  $p < 0.05$  considered statistically significant. In cases where the data distribution is not normal, the Wilcoxon signed-rank test will be employed.

7.3 Descriptive Statistics for Adverse Events: Descriptive statistics, reported as percentages, will be used to analyze adverse events after using the serum with Epidermal Growth Factor.

7.4 Descriptive Statistics for Participant Satisfaction: Descriptive statistics, reported as percentages, will be used to analyze participant satisfaction after using the serum with Epidermal Growth Factor.

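### The allergy exclusion covers serum components only, so a volunteer with a known allergy to the study sunscreen (or, less importantly, the supplied soap) is eligible as written

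*Combined protocol and SAP*

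**What the plan says.** - **Eligibility.** Section 1.4, item 1, excludes "Individuals with allergies to components tested in the serum". The nearest other criterion is item 3, "Acute or chronic skin conditions causing inflammation, such as Eczema or Atopic dermatitis". Nothing else in sections 1.3 or 1.4 mentions allergy to a supplied product.
- **Sunscreen.** Section 2.1, step 9, states that after the morning serum "participants will apply Skin Intelligence Sunscreen Cream SPF30 PA+++, using 2 fingertip units (approx. 1 gram) each time". In the table of activities (section 4), the row "Apply sunscreen cream" is ticked from d1 to week 16, while the serum row is ticked only to week 8.
- **Soap.** Section 2.1, step 5: "Volunteers are advised to cleanse their skin lightly with the provided soap before testing".
- **Product information.** Section 3 lists the composition of the serum and describes safety testing of the tested product. It gives no ingredients for the sunscreen or the soap.
- **Reactions.** The Note at the end of section 2.1 says: "If adverse events occur or if there are signs of an allergic reaction, participants will cease product usage". It does not say which product is meant.
- **Reporting.** Section 6.2 collects rash, irritation, infection and new pigmented spots. Section 7.3 summarises these as percentages of "adverse events after using the serum with Epidermal Growth Factor". No section asks for the suspected product.

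**The concern.** The allergy exclusion exists to keep people away from something they are known to react to. It covers one of the three products the study supplies. The most important omission is the sunscreen, which stays on the skin and is applied daily as a study requirement. The soap matters less, because it is advised, not required, and only before testing.

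Two things are at stake. The first is avoidable exposure of a volunteer whose allergy was known at screening. The second is a small loss of clarity in the adverse event summary. Rash and irritation are the events a contact reaction would produce, and section 7.3 has no means of separating those suspected to come from the sunscreen or soap from those suspected to come from the serum. The single-group design adds no vehicle or sunscreen-only arm that would show a background rate.

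**Working it through.** The plan states no figure on this point, so there is nothing to reproduce. The check compares the text on eligibility, exposure and reporting, followed by arithmetic on scale.

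**Step 1: is such a volunteer eligible?** Take a person with clear skin and a known allergy to a sunscreen ingredient. Item 1 does not apply unless the ingredient is also in the serum. Item 3 concerns inflammatory skin disease; a known allergy without present disease does not clearly meet it. No other item applies, so the person is eligible as written.

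**Step 2: how much exposure does the study cause?**

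| Product | Source | Planned exposure |
|---|---|---|
| Serum | Section 2.1 step 8; section 4 | Twice daily to week 8 |
| Sunscreen, by the table | Section 4 | 16 × 7 = 112 mornings, of which 8 × 7 = 56 follow the end of serum |
| Sunscreen, by the step text | Section 2.1 step 9 | Tied to the morning serum, hence 8 × 7 = 56 mornings |
| Soap | Section 2.1 step 5; section 4 | Advised before testing; four measurement visits (d1, weeks 8, 12 and 16) |

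The two sunscreen rows differ, and the sponsor should reconcile them. The eligibility gap exists on either reading. If the table governs, events found at weeks 12 and 16 could arise when sunscreen is the only one of the two daily products still in use, yet they would fall under the section 7.3 description.

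**Step 3: what does one such event do to the reported rate?** Inputs: N = 28 (section 1.2), all 28 in the denominator, each affected person counted once.

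- One person: 1/28 = 3.6% (exact 95% interval 0.1% to 18.4%).
- Two people: 2/28 = 7.1% (exact 95% interval 0.9% to 23.5%).

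**Step 4: how likely is it that at least one is enrolled?** The documents give no prevalence of sunscreen or soap allergy. For assumed prevalence p, with no self-exclusion by people who know of their allergy, the chance is 1 − (1 − p)^28:

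| Assumed p | Chance of at least one in 28 |
|---|---|
| 0.5% | 13% |
| 1% | 25% |
| 2% | 43% |
| 5% | 76% |

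These rows only illustrate a range. People who know they react to sunscreen may well decline, so the true chance would be lower than the table gives at any p.

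**The case against.** The best case on the other side is that several existing steps would probably stop such a person. A screener could stretch item 3 to cover contact allergy. Relevant personal data are collected at the preparation meeting (section 2.1, step 1). Section 5 requires methods and risks to be explained before consent, so a volunteer who knows of the allergy can decline. Adverse effects are checked by video call at weeks 2 and 4, and product use ceases on signs of allergy. This lowers the likelihood, but none of these steps requires exclusion, and the last two act only after exposure.

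Four stronger readings are tempting, and the documents do not support them.

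- *A reader might infer that section 7.3 attributes every event to the serum.* Its wording is temporal, not causal, and it does not prevent the investigator from noting a suspected product. What stands is that the plan does not ask for one.
- *A reader might treat the soap as equal to the sunscreen.* It is advised, and only before testing.
- *A reader might infer that anyone who reacts is lost from follow-up.* The Note gives removal from the study only as a possibility, and only for severe reactions.
- *A reader might infer that rewording exclusion 1 cures the reporting problem.* It removes known allergies only. New sensitisation, unrecognised allergy and simple irritation from the sunscreen would still be counted in the same way.

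Any error here would overstate, not hide, events linked to the serum, and it would do so in a descriptive secondary outcome. That objection stands and limits the weight of the point.

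**Conclusion.** The gap in the wording of exclusion 1 is real: a known allergy to the study sunscreen, or less importantly the soap, does not exclude a volunteer, and the study would then expose that person to it. Any resulting rash or irritation adds 3.6 points per person to the percentages in section 7.3, assuming a denominator of 28. How often this would happen cannot be stated from the documents.

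It might also be inferred that inflamed skin would distort the primary moisture, water-loss or melanin readings enough to matter. This is possible for an affected individual, but nothing in the documents allows its size to be estimated, and the point does not rest on it. This is a modest, inexpensive improvement to participant safety and does not threaten the trial's main conclusions. It rests on the supplied text; the consent pages and one other part were not available and might address product allergy.

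**What to change.** 1. Reword exclusion 1 to: *known allergy to any component of the EGF serum, the study sunscreen or the provided soap*. At screening, check the answer against the ingredient lists of all three products.
2. Add a field for the suspected product (serum, sunscreen, soap, other, unknown) to each adverse event record. In section 7.3, report all events and, separately, those with the serum as a suspected cause.
3. Reconcile section 2.1 step 9 with the table of activities on sunscreen use after week 8, so that each event can be set against the products in use at the time.

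Cost: one screening question, obtaining the sunscreen and soap ingredient lists (not in the supplied text), one extra adverse event field, and possibly one or two more screen failures. The design, the sample size and the primary analysis are unchanged.

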## **2. Research Format**

Pilot study and one group before-after design.

### **2.1 Research Operation Steps**

#### **1) Volunteer Preparation Phase**

Selection of volunteers based on inclusion and exclusion criteria.

Schedule a meeting to provide information about the research to the volunteers.

Collect personal and relevant research-related data from volunteers during the meeting.

#### **2) Inter-rater Reliability Assessment**

Two dermatologists will review approximately 20 images of the sample group.

Assess inter-rater reliability and calculate the Interclass Correlation Coefficient (ICC).

If ICC is less than 0.75, both assessors will meet to align their evaluations before the actual research begins.

#### **3) Skin Condition Measurement for Volunteers**

Volunteers receive appointments for skin condition measurements. Skin measurements occur at the same time each week. Rescheduling is allowed for volunteers unable to make appointments due to non-study-related commitments or COVID-19 concerns.

#### **4) Laboratory Location**

The research will be conducted at the Biogenomics Laboratory on the 4th floor of the Queen Sirikit National Institute of Child Health, Monday to Friday.

#### **5) Skin Cleaning Instructions for Volunteers**

Volunteers are advised to cleanse their skin lightly with the provided soap before testing. Cleaning conditions are standardized to maintain consistency across all tests.

## 6) Evaluation Parameters

Five parameters will be measured using various tools to assess experiment results.

Measurement of skin moisture and water loss using Corneometer and Tewameter, respectively.

Measurement of skin elasticity using Cutometer.

Measurement of skin color using Mexameter.

Evaluation of skin wrinkles using Visioscan.

[figure not shown]
Assessment of facial skin changes using Visia-CR imaging.

These steps are meticulously designed to ensure high-quality and reliable data for the dermatological research.

The measurements for Corneometer, Tewameter, and Cutometer will be taken at four specific positions:

- Right Malar prominence area
- Left Malar prominence area
- Central forehead
- Central chin

Measurements will be performed three times at each position, as illustrated in the diagram below. Each volunteer will calculate the average value for all four areas to represent their data. Assessors will use a marking technique on transparent sheets to ensure consistent measurement points are maintained across all sessions.

[figure not shown]

The positions for measurements using Corneometer, Tewameter, and Cutometer

When using the Mexameter to measure the Melanin Index (MI), readings will be taken at two specific positions:

- Right Malar prominence area
- Left Malar prominence area

Measurements will be conducted three times at each position, as depicted in the diagram below. Each volunteer will calculate the average value for both areas to represent their data. Assessors will utilize a marking technique on transparent sheets to ensure consistent measurement points across all sessions.

The positions for measurements using Mexameter

Visioscan is used to assess wrinkles using a 4-grade percentage wrinkle improvement scale as follows:

Grade 1 (0-25%): No change to a slight improvement in wrinkles.

Grade 2 (> 25-50%): Moderate improvement in wrinkles.

[figure not shown]
Grade 3 (50-75%): Marked improvement in wrinkles.

Grade 4 (>75%): Significant to no wrinkles.

The assessment involves scoring at four positions:

- Right crow feet area
- Left crow feet area
- Right cheek line area
- Left cheek line area

Positions are determined based on Hamilton's classification of contour changes of facial skin, specifically targeting static wrinkles effectively. Volunteers will calculate the average value for both areas to represent their data. The assessment will be performed by two board-certified dermatologists, each evaluating both areas, ensuring a thorough and reliable evaluation of wrinkle improvement.

The positions for measurements using Visioscan

Visia-CR is utilized as a detailed facial imaging system to compare changes before and after product usage. The assessment is done by comparing images using the Subject Global Aesthetic Improvement Scale (SGAIS) as follows:

Score 1: Worse (no improvement)

Score 2: Mild improvement (<25% improvement)

Score 3: Improvement (25-49% improvement)

Score 4: Much improved (50-74% improvement)

Score 5: Very much improved (75% improvement or more)

The evaluation is conducted by two board-certified dermatologists, each specializing in skin health. The images captured by Visia-CR allow for a thorough comparison of facial conditions before and after product usage, providing a detailed understanding of the product's impact on the skin's aesthetic improvement.

The medical technicians will perform measurements of skin moisture, water loss, skin elasticity, skin color, and capture facial images using a specialized imaging device, taking approximately 30 minutes for each

participant. This research will measure these parameters on the first day (d1) before applying EGF serum to establish a baseline.

7) Baseline Measurements:

Participants will undergo measurements on the first day, assessing moisture, water loss, skin elasticity, skin color, and facial images using Corneometer, Tewameter, Cutometer, and imaging devices.

8) Application of EGF Serum:

Participants will apply EGF serum twice daily for 8 weeks, using three drops each time, covering the entire face.

9) Sunscreen Application:

After using EGF serum in the morning, participants will apply Skin Intelligence Sunscreen Cream SPF30 PA+++, using 2 fingertip units (approx. 1 gram) each time.

10) Second Visit (2 Months):

Participants return for a second assessment after 2 months, with measurements conducted similar to the baseline.

11) Subsequent Visits:

Participants stop using the serum and return for measurements in the 3rd and 4th months, following the same procedure.

Note:

If adverse events occur or if there are signs of an allergic reaction, participants will cease product usage and receive standard treatment from the institute. Severe reactions may lead to the participant's exclusion from the study.

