**Visioscan VC98:**

Manufacturer: Courage & Khazaka (C&K) Electronic GmbH, Germany

Purpose: Measures skin wrinkles.

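### Wrinkles are scored only as improvement since baseline, with no day-1 score and no grade for worsening, so the score does not fit the planned before-after test

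*Combined protocol and SAP*

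**What the plan says.** - **Outcome and test.** Section 6.1 makes wrinkle assessment one of five primary parameters, due at baseline and at 2, 3 and 4 months. Section 7.2 compares it before and after serum, at 8, 12 and 16 weeks, by repeated-measures ANOVA with p < 0.05, or by the Wilcoxon signed-rank test if the data are not normal.
- **Scale.** Section 2.1, step 6: "Visioscan is used to assess wrinkles using a 4-grade percentage wrinkle improvement scale as follows". The lowest level is "Grade 1 (0-25%): No change to a slight improvement in wrinkles"; the highest is improvement above 75%. Two dermatologists score it. Four facial positions are listed, followed by "Volunteers will calculate the average value for both areas to represent their data".
- **Schedule.** In section 4, the row "Measuring wrinkle using Visioscan" is ticked at d1, 8, 12 and 16 weeks. The row "Evaluation by Specialists (Two Board-Certified Dermatologists" is ticked at 8, 12 and 16 weeks only.
- **Device.** Section 3 says of the Visioscan VC98: "Purpose: Measures skin wrinkles". It names no output variable.
- **Day-1 list.** Section 2.1, step 7 describes the baseline session as "assessing moisture, water loss, skin elasticity, skin color, and facial images using Corneometer, Tewameter, Cutometer, and imaging devices". Wrinkles are not named.
- **Other scales.** Section 1.3 uses a wrinkle severity scale (grades 2 to 3) for eligibility. Section 4 does not schedule it again and section 7.2 does not analyse it. The global aesthetic scale (SGAIS) applied to the Visia-CR images begins at "Score 1: Worse (no improvement".

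**The concern.** A grade of percentage improvement is already a comparison with baseline. It cannot have a value on day 1, and the schedule confirms that no dermatologist grades anyone then. Section 7.2 nevertheless needs a day-1 value to compare with the later ones. The scale also stops at no change, so a participant whose wrinkles become worse than at baseline is recorded with those who did not change.

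Two things are at stake. A primary parameter has no defined variable that fits its planned test, so the analyst would have to choose one, possibly after seeing the data. The simplest choices that keep the grades also give a test that can only point towards improvement. The design has one group and no control (section 2), so the before-after comparison is the only evidence of efficacy. Serum stops after 8 weeks. Partial loss of benefit can still be seen at 12 and 16 weeks (for example Grade 3 falling to Grade 1), but a fall below baseline cannot.

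**Working it through.** The plan gives no figure to reproduce: section 1.2 sets 28 participants as a pilot number, without power, effect size or SD. The check is therefore what happens when the grades are put into the planned test. Tests are taken as two-sided, which the plan does not state.

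**1. Grades as written.** Scores exist at 8, 12 and 16 weeks. These can be compared with each other, but there is no before-after pair.

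**2. Day 1 coded 0.** Every later grade is at least 1, so all 28 differences are positive even if nobody changes. Exact signed-rank p = 2/2^28 = 7.5 × 10⁻⁹.

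**3. Day 1 coded Grade 1.** Differences can only be zero or positive. With k positive differences and none negative, zeros dropped, exact p = 2/2^k:
- k = 5: 2/32 = 0.0625
- k = 6: 2/64 = 0.031

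Six of 28 participants above Grade 1 are enough, whatever happened to the other 22.

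**4. The same participants on a measure that records worsening.** With changes of equal size, the signed-rank test reduces to the sign test:
- 6 better, 22 worse: p = 2 × P(Bin(28, 0.5) ≤ 6) = 0.0037, in favour of worsening
- 6 better, 6 worse, the rest unchanged: p = 1.0

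**5. False positives with no true change, day 1 coded Grade 1.** Let e be the chance that one rating is a grade too high, ρ the correlation between a participant's ratings (equicorrelated latent normal), and m the number of ratings averaged. A participant counts as positive if at least one rating is too high, with probability q; when ρ = 0, q = 1 − (1 − e)^m. The false-positive rate at one visit is P(Bin(28, q) ≥ 6). For example, m = 8, e = 5%, ρ = 0 gives q = 1 − 0.95^8 = 0.337 and a rate of 94.7%.

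The plan gives neither e nor ρ, so both are assumed. It also leaves m unclear: 4 positions × 2 raters = 8, or two areas × 2 raters = 4.

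| m | ρ | e = 1% | e = 2% | e = 3% | e = 5% |
|---|---|---|---|---|---|
| 8 | 0 | 1.8% | 23.2% | 58.4% | 94.7% |
| 8 | 0.5 | 0.4% | 6.4% | 21.4% | 59.8% |
| 8 | 0.8 | 0.04% | 0.8% | 3.9% | 19.2% |
| 4 | 0 | 0.07% | 1.9% | 9.4% | 42.1% |
| 4 | 0.5 | 0.03% | 0.7% | 3.9% | 20.8% |
| 4 | 0.8 | 0.01% | 0.2% | 1.0% | 6.9% |

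The table shows only that the 5% level is not controlled. It does not show that a false positive is likely in this trial.

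**6. Contrast with a signed measure.** With a signed percentage change, true change 0 and assumed noise SDs of 10 to 30 percentage points per rating (eight independent ratings averaged), a simulated one-sample t-test on 28 participants rejected in 3.9% to 5.2% of runs (2,000 runs per SD).

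**The case against.** The strongest reply is that a day-1 wrinkle measurement is planned. Section 4 ticks the Visioscan on day 1 in a row separate from the specialists' row, section 3 says that the device measures wrinkles, and section 6.1 promises baseline measurement. The day-1 list in section 2.1, step 7 is weak evidence the other way: it is plainly incomplete, since it mentions skin colour but not the Mexameter, and its imaging devices could include the Visioscan. All of that stands. A day-1 acquisition should exist, and a device reading would fit the test. What is missing is the value to be taken from it. No numeric parameter is named, and step 6 ties the Visioscan to the improvement grades.

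The eligibility severity grade does give each participant a wrinkle grade at entry, but it is not repeated. The rater-agreement step in section 2.1 (step 2) supplies neither a day-1 score nor a grade for worsening.

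It is also fair to say that the one-directional test arises only if the grades are tested with an assumed day-1 code, that 22 participants getting worse is an extreme case, and that the false-positive range rests wholly on assumed inputs. The case therefore rests on the missing variable and the missing grade, not on that range. The pilot status and the four unaffected measures limit the reach of the problem, but section 7.2 still attaches a significance test to this parameter.

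**Conclusion.** The concern holds, and the plan is wrong as written on this point. It should be corrected before wrinkles are analysed. One of five primary parameters has no defined variable that fits its planned test. Following the stated scale leaves either no before-after pair or, with a day-1 code of 0 or Grade 1, differences that cannot be negative. Under the Grade 1 code, six of 28 participants are enough for p = 0.031 regardless of the rest. That figure assumes an exact two-sided test; the contrasting 0.0037 also assumes changes of equal size. The defect itself follows from the text and needs no assumption about rating error.

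The moisture, water-loss, elasticity and colour analyses are not affected. The merging of worse with unchanged in SGAIS Score 1 is a reporting matter only, because section 7.2 does not list SGAIS among the tested measures.

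**What to change.** In section 2.1, step 6 and section 7.2, define one wrinkle variable recorded in the same way at d1, 8, 12 and 16 weeks, and test change from d1 on it. There are two ways:

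1. **A prespecified quantitative Visioscan parameter.** This is the simpler choice. The device is already scheduled at all four times, so the cost is protocol and SAP wording only.
2. **Absolute wrinkle severity graded by the same two dermatologists from the scheduled images**, for example on the severity scale named in section 1.3. The raters should not know which visit an image comes from, since the trial has no control group. The cost is up to 28 × 4 positions × 2 raters = 224 ratings per visit, or 224 × 4 = 896 in all.

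With either choice, add a category for worsening to the improvement scale and report those grades as percentages at each visit, without a before-after p-value. For descriptive reporting, split SGAIS Score 1 into worse and no change. Also state whether the participant's value averages four positions or two areas. No new visit, device or staff is needed.

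### The Visia-CR score puts worsening and no change in one lowest level, so with no true effect, rating error can only raise this primary-outcome score, and worsening is hidden

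*Combined protocol and SAP*

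**What the plan says.** Section 2 (Research Format) gives the design as "Pilot study and one group before-after design", and section 1.2 sets the size at 28. Section 6.1 lists both wrinkle assessment and Visia-CR facial imaging in the primary outcome.

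For Visia-CR, section 2.1, item 6 says: "The assessment is done by comparing images using the Subject Global Aesthetic Improvement Scale (SGAIS) as follows". The lowest level is "Score 1: Worse (no improvement". Score 2 is improvement below 25%, and scores 3 to 5 begin at 25%, 50% and 75%. Two dermatologists rate the before and after images.

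For wrinkles, the lowest level is "Grade 1 (0-25%): No change to a slight improvement in wrinkles", and Grades 2 to 4 are larger improvements. Four facial positions are scored by two dermatologists.

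In the table of activities (section 4), the row "Evaluation by Specialists (Two Board-Certified Dermatologists" is ticked at weeks 8, 12 and 16 but not on day 1. The Visioscan wrinkle measurement is ticked on day 1 as well as at those weeks. Section 7.2 covers wrinkle assessment before and after serum use and does not name the Visia-CR score. The only rater safeguard described is the agreement check (ICC) in section 2.1, item 2.

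**The concern.** A change scale needs room on both sides of no change. On the Visia-CR scale no change sits at the floor. A rater who misjudges an unchanged face as slightly better records 2; one who misjudges it as slightly worse still records 1. The errors cannot cancel within a participant or across participants, and there is no control arm in which the same upward error would appear. True worsening is also recorded as 1.

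The missing masking is a separate problem that pushes the same way. Raters who know which image follows serum use may expect improvement. The ICC check does not address this, because two raters who share an expectation can agree well and both be biased.

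At stake is a primary result that could show some mild benefit when there is none, and that would be carried from the pilot into later work.

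**Working it through.** **Inputs from the documents.** Visia-CR cut-points at 25%, 50% and 75%, with score 2 for any smaller improvement; wrinkle cut-points at 25%, 50% and 75%; 28 participants; three rated visits; two raters; four wrinkle positions. The plan gives no effect size, SD or power for the 28, so there is no planned figure to reproduce.

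**Assumptions.** The documents give neither a rating error nor a rule for calling a face unimproved. I take perceived change as true change plus normal error with SD 5, 10, 15 or 20 points, and let a rater call improvement only above a band b of 0, 5 or 10 points.

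**Step 1: Visia-CR, true change 0.** P(score ≥ 2) = P(error > b) = 1 − Φ(b/SD). P(score ≥ 3) = 1 − Φ(25/SD), and likewise at 50 and 75. Mean score = 1 + P(≥2) + P(≥3) + P(≥4) + P(5).

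| Band b | Quantity | SD 5 | SD 10 | SD 15 | SD 20 |
|---|---|---|---|---|---|
| 0 | P(≥2) | 0.500 | 0.500 | 0.500 | 0.500 |
| 0 | Mean | 1.50 | 1.51 | 1.55 | 1.61 |
| 5 | P(≥2) | 0.159 | 0.309 | 0.369 | 0.401 |
| 5 | Mean | 1.16 | 1.31 | 1.42 | 1.51 |
| 10 | P(≥2) | 0.023 | 0.159 | 0.252 | 0.309 |
| 10 | Mean | 1.02 | 1.16 | 1.30 | 1.42 |
| any | P(≥3) | 0.000 | 0.006 | 0.048 | 0.106 |

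Example, SD 20 and b = 10: 1 + 0.309 + 0.106 + 0.006 + 0.000 = 1.42. Most of the excess is score 2. Averaging over raters reduces the spread of these values but not their mean.

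**Step 2: Visia-CR, every face truly worse by 15%.** Each cut-point is now 15 points further away. At SD 20 and b = 0: P(≥2) = 1 − Φ(15/20) = 0.227, P(≥3) = 1 − Φ(40/20) = 0.023, P(≥4) = 0.001, so the mean is 1.25. At SD 5 and b = 10 it is 1.00. A signed scale with the same bands mirrored below zero would average −0.82 to −1.03 over the same grid, and exactly 0 when true change is 0.

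**Step 3: wrinkle grade, true change 0.** A rating leaves Grade 1 only if the error exceeds 25 points: 0.000, 0.006, 0.048 and 0.106 at SD 5, 10, 15 and 20. The mean grade is 1.00, 1.01, 1.05 and 1.11.

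**Step 4: a minimal repair.** Score worse as −1 and no change as 0. If the improvement levels are renumbered 1 to 4, the null mean is P(≥2) + P(≥3) + P(≥4) + P(5) − P(error < −b). The first and last terms cancel, leaving 0.00, 0.01, 0.05 and 0.11 at SD 5 to 20. If the numbers 2 to 5 are kept, P(≥2) is added back and the null mean returns to 0.02 to 0.61. Splitting wrinkle Grade 1 into 0 and −1 gives P(>25) + P(>50) + P(>75) − P(error < −b), which runs from −0.02 (SD 5, b = 10) to −0.50 (SD 5, b = 0): a downward bias larger than the upward one it replaces.

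All these figures come from the shape of the scales. Masking would not change them, and expectation bias is additional and not quantified.

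**The case against.** This is a 28-person pilot and the size is set by assumption: the share scoring 2 or more runs from 2% to 50%, and 50% requires raters who never see a face as unchanged. That stands. The direction needs no SD, but the size cannot be read from the documents.

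A reader might infer more than the documents support, in four ways:

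- **A near-certain false-positive test.** Testing the score against a constant of 1 would often reject with no true effect, but the plan contains no such test.
- **Equal bias in the wrinkle grade.** Step 3 shows that Grade 1 absorbs errors of up to 25 points. The main loss there is that worsening cannot be recorded.
- **A wrinkle comparison with no baseline.** The dermatologist grade has no day-1 value, but Visioscan is scheduled on day 1, so 7.2 could rest on a device reading. The text is unclear rather than shown to be wrong.
- **A trial blind to harm, or masking known to be absent.** Moisture, water loss, elasticity and melanin readings move both ways, and irritation, rash, new dark spots and infections are collected as adverse events. Masking is not described; that does not prove it will not be done.

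Pilot status does not remove the point: a score that errs in one direction passes an inflated estimate to the next study.

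**Conclusion.** The point holds for the Visia-CR score. With no true effect, rating error can only raise it, and worsening is indistinguishable from no change. Under the stated assumptions the null mean is 0.02 to 0.61 above the floor, and a uniform 15% worsening would read as no change to slight benefit. The harm is to how a primary outcome is reported, not to a planned p-value.

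The wrinkle grade shares the inability to show worsening, with negligible upward bias at error SD 10 or less and an excess of 0.05 to 0.11 at SD 15 to 20. Which wrinkle quantity 7.2 analyses needs to be stated. The repair is cheap and should be made, but the flaw does not undermine the instrument-based outcomes.

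**What to change.** 1. **Visia-CR.** After the last visit, show each baseline and follow-up pair undated, in random left-right order, shuffled across participants and visits. Each dermatologist records which image is better, or no difference, and by how much, using the plan's percentage bands always relative to the worse-looking image. After ratings are locked, decode to a signed score from −4 to +4, with 0 for no difference. Report the mean with a 95% confidence interval at weeks 8, 12 and 16. If it is tested, use a Wilcoxon signed-rank test against 0. With 28 participants and zero true change, the interval half-width would be 0.06 to 0.36 if the two raters' errors are independent and 0.08 to 0.50 if they are identical, on the same assumptions.
2. **Wrinkles.** If the dermatologist grade is kept, rate order-masked image pairs (assuming day-1 and follow-up images are stored) with mirrored cut-points: a central grade 0 for changes within 25% either way, and grades beyond 25% in each direction. State in 7.2 whether this grade or the Visioscan reading with its day-1 value is analysed.
3. **Minimal alternative, Visia-CR only.** Worse = −1, no change = 0, and the four improvement levels renumbered 1 to 4. The renumbering is essential. Do not split wrinkle Grade 1 into 0 and −1 (step 4).

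**Cost.** Same images, dermatologists and visits; image relabelling, a randomised viewing list and a new score sheet. The load is 28 × 3 × 2 = 168 Visia-CR pair ratings and up to 28 × 4 × 3 × 2 = 672 wrinkle-site ratings. Reading moves to after week 16, and scores are no longer directly on the plan's scales. Masking reduces expectation bias but does not fully remove it, because each baseline image recurs in three pairs.
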